7.4 Invasive Procedures

The planned invasive procedure will be performed in the Post-treatment period between Days 9 and 14. The need for the invasive procedure will be reassessed in the event of the following:

- Platelet count $\geq 200 \times 10^9/L$
- Administration of an antithrombotic drug
- In the opinion of the investigator, the procedure is no longer in the patient's best because of an AE or other concern
- The patient requests cancellation of elective procedure after randomisation

If any of the above criteria are met and the elective procedure cannot be performed between Days 9 and 14, it may be performed up to Day 35 of the study. If a patient does not undergo a procedure, all relevant follow-up assessments should be performed and data should be collected up to Day 35. In case the invasive procedure performed between Days 9 and 14 needs to be repeated, the same procedure may be performed after Day 15 according to the discretion of the investigator.

Information on whether to perform the planned invasive procedure, details of the procedure performed (eg, percutaneous radiofrequency ablation [RFA]/microwave coagulation therapy [MCT], laparoscopic RFA/MCT, endoscopic variceal ligation [EVL], endoscopic injection sclerotherapy [EIS], TACE, TAE, or other), the date performed, the initiation time of the procedure, and whether the procedure was performed within the specified period will be recorded on the CRF. If the planned invasive procedure is not performed within the specified period or is not performed at all, the reason will be recorded on the CRF.

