7.7.2 Portal Vein Thrombosis

Portal vein thrombosis will be assessed by the investigator or designee using diagnostic imaging (ultrasonography, CT, or MRI) during the Screening period, and between 3 and 10 days after the planned invasive procedure* in the Post-treatment period (Days 12 to 21). For assessment in the Screening period, the investigation should be arranged as close to randomisation as possible. However, for patients in whom gastro-oesophageal varices are treated, portal vein thrombosis will be confirmed using imaging performed after the treatment.

The imaging date and method, and the presence or absence of portal vein thrombosis will be recorded on the CRF. The independent safety committee will assess portal vein thrombosis (see Section 9.8.2).

* Even if the planned invasive procedure is postponed. In addition, if any additional invasive procedures are performed, diagnostic imaging should also be performed before and after the additional procedure for post-assessment of the initial and additional procedures.

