7.7.4 WHO Bleeding Scale

The severity of bleeding will be assessed according to the WHO Bleeding Scale (see Appendix 7)[15] during the Screening period, on Days 1 and 8, between 3 and 10 days after the invasive procedure (Days 12 to 21), and on Day 35 (or early termination of assessment, if applicable). The date of the assessment and the grade will be recorded on the CRF.

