6.3 Analysis Visit

Analysis visit windows are defined as shown in Table 1 to determine the analysis value for each study visit. Measurements collected outside of the visit window will be considered missing for that study visit. For all patients with multiple values within a visit window, the value obtained closest to the target study day will be used. In the case of multiple observations equidistant to the study visit date, the later one will be used, unless otherwise noted. Only for screening visit, the earliest one will be used for analysis if multiple values were obtained within 28 days prior to randomization.

In regard to “after the invasive procedure”, which is the analysis visit for WHO Bleeding Scale, Portal Vein Thrombosis, and Portal Blood Flow, the allowance is within 3 days to 10 days after the first invasive procedure. In the case of multiple observations equidistant to the study visit date, the earlier one will be used, unless otherwise noted.

Table 1 Analysis Visit Windows

Study Day for Analysis	Allowance
Screening	Within 28 days prior to randomization
Day 1 (Baseline)	Within 7 days before initiation of study medication
Days 5-7	± 0 day
Day 8	± 0 day
Day 10	± 1 day
Days 12 and 14	+1 day
Days 17 and 21	-1 day to +2 days
Day 28	± 2 days
Day 35	-2 day to +7 days

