10.7 Portal Vein Thrombosis and Portal Blood Flow

For the patients who underwent diagnostic imaging in safety analysis population, the number and proportion of patients who experienced portal vein thrombosis at screening and after the primary invasive procedure will be calculated by treatment group. The patients who underwent an invasive procedure more than once will be regarded as having portal vein thrombosis if they experienced it at least once after the primary invasive procedure. If a patient received an invasive procedure and underwent assessment of portal vein thrombosis on the same day, the assessment will be considered as being after invasive procedure (see [Section 6.3](#)).

For the patients who underwent Doppler ultrasonography in safety analysis population, summary statistics by category for the direction of portal blood flow (i.e., hepatofugal, hepatopetal, stasis) at screening and after the primary invasive procedure will be calculated by treatment group. If a patient received an invasive procedure and underwent Doppler ultrasonography on the same day, the assessment will be considered as being after invasive procedure (see [Section 6.3](#)).

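### SAP 10.7 counts a same-day portal vein scan as post-procedure, but the window it cites in SAP 6.3 starts at day 3; separately, the protocol's Days 12 to 21 does not match its own 3–10 day rule

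*SAP*

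**What the plan says.** **SAP 6.3 (Analysis Visit)** defines one post-procedure visit for the WHO Bleeding Scale, portal vein thrombosis and portal blood flow: "the allowance is within 3 days to 10 days after the first invasive procedure". The same section makes measurements outside a visit window missing for that visit.

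**SAP 10.7** tabulates portal vein thrombosis and flow direction at screening and after the primary procedure. If the scan or Doppler took place on the day of a procedure, "the assessment will be considered as being after invasive procedure", with a cross-reference to 6.3. For patients with more than one procedure, a thrombosis seen at any point following the primary one counts, and no day limit is restated.

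**Protocol 7.7.2** schedules the thrombosis imaging "between 3 and 10 days after the planned invasive procedure* in the Post-treatment period (Days 12 to 21"), and a footnote applies this "Even if the planned invasive procedure is postponed". Section 7.7.3 gives the same timing for portal flow. Section 7.7.4 schedules the bleeding scale "between 3 and 10 days after the invasive procedure (Days 12 to 21"). Footnote g of the schedule (Appendix 1) gives 3 to 10 days with no calendar range.

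**Protocol 7.4** fixes the procedure days: "The planned invasive procedure will be performed in the Post-treatment period between Days 9 and 14". If the procedure is postponed, "it may be performed up to Day 35 of the study".

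**The concern.** The same-day rule in SAP 10.7 cites a section that contains no such rule and whose window excludes day 0. Two programmers could handle the same scan differently: one enters it as the post-procedure result, the other sets it to missing.

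The rule does not use clock time. If it governs, a scan done hours before the procedure, or just after it, can stand as the post-procedure result with no observation time behind it. A negative result of that kind says little about thrombosis following the procedure.

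The counting rule is also uneven. Repeat-procedure patients count whenever a later thrombosis is seen, while for single-procedure patients the only stated definition of the visit is days 3–10.

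In the protocol, a site that schedules by the calendar range can miss the 3–10 day rule, and a site that follows the rule can fall outside the range. Portal vein thrombosis is named as an event of special interest (protocol 7.8.8.1), so its imaging table should have a single reading.

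**Working it through.** **1. The two SAP rules side by side (portal vein thrombosis)**

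| Scan, days after first procedure | SAP 6.3 visit | SAP 10.7, one procedure | SAP 10.7, repeat procedures |
|---|---|---|---|
| 0 | outside, missing | counted as after | counted as after |
| 1–2 | outside, missing | no separate rule, so 6.3 applies | a thrombosis counts |
| 3–10 | inside | counted | a thrombosis counts |
| over 10 | outside, missing | no separate rule, so 6.3 applies | a thrombosis counts |

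The first row is a direct conflict. The second and fourth rows treat the two kinds of patient differently. The exception clause in 6.3 (unless otherwise noted) is attached to the choice among multiple observations, not to the 3–10 day allowance, so it does not clearly make 10.7 an exception. The window also has no target day, so the 6.3 rules on the closest or equidistant value have nothing to work from there.

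**2. The protocol's calendar range**

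Inputs: procedure day p = 9 to 14 (protocol 7.4); offset 3 to 10 days (protocol 7.7.2–7.7.4).

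Formula: the window for procedure day p runs from p + 3 to p + 10.

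- Lower limit: 9 + 3 = 12. This reproduces the stated Day 12.
- Upper limit: 14 + 10 = 24. The stated Day 21 is not reproduced. It arises as 11 + 10 or 14 + 7, and neither is the stated rule for Days 9–14.

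| Procedure day | 3–10 days after |
|---|---|
| 9 | 12–19 |
| 10 | 13–20 |
| 11 | 14–21 |
| 12 | 15–22 |
| 13 | 16–23 |
| 14 | 17–24 |

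Day combinations that follow the 3–10 day rule: 6 procedure days × 8 offsets = 48. Those after Day 21: 1 (procedure Day 12) + 2 (Day 13) + 3 (Day 14) = 6, and 6/48 = 12.5%.

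Day combinations inside Days 12–21: 6 procedure days × 10 scan days = 60. Those outside 3–10 days: 3 before the procedure + 3 on the same day + 9 at 1–2 days + 3 at 11–12 days = 18, and 18/60 = 30%.

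These are counts of day combinations, not proportions of patients.

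**3. Postponed procedures**

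The whole window lies after Day 21 when p + 3 > 21, that is, from procedure Day 19 onward. A procedure on Day 35 gives 35 + 3 = 38 to 35 + 10 = 45.

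**The case against.** The strongest reply is that little can be lost. Thrombotic and thromboembolic adverse events are summarised under SAP 10.2 with no 3–10 day limit. Adverse events are collected up to the last follow-up visit, or 28 days from the last dose if that is later (protocol 7.8.2). The Independent Safety Committee also assesses portal vein thrombosis (protocol 7.7.2, 9.8.2). A thrombosis reported as an adverse event therefore stays in the safety analysis, and at most it leaves the imaging table of SAP 10.7. This stands, and it limits the point to that table.

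A reader might also infer more than the documents support:

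- *That thrombosis and bleeding assessments have three conflicting schedules.* The same-day text covers only portal vein thrombosis and portal flow; SAP 10.3 has no such rule for the bleeding scale. The text also classifies scans as before or after and is not a schedule.
- *That Days 12 to 21 removes scans from the analysis.* The SAP never uses it as an analysis window and would accept a Day 22–24 scan that is 3–10 days after the procedure. A Day 20 scan after a Day 9 procedure (20 − 9 = 11 days) breaks the 3–10 day rule in the same protocol sentence, so the SAP applies that rule when it excludes the scan.
- *That scans are in fact wrongly counted or dropped.* The documents show an unresolved choice between two rules, and give no count of same-day scans.
- *That one lost case would halve the rate.* The nearest figure is 2.1% per group in the Japanese phase 3 study (1 of 48, protocol 1.3), or about 2 per 100. It covers all thrombotic events; the documents give no rate for portal vein thrombosis in this table.
- *That same-day scans should simply be labelled pre-procedure.* The table has only a screening column and a post-procedure column, so a same-day positive would then appear in neither.

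**Conclusion.** Three defects hold. First, SAP 10.7 and 6.3 give different answers for a portal vein or Doppler assessment on the procedure day, and the SAP does not say which governs. Second, thromboses imaged on days 1–2 or after day 10 may be absent from the imaging table for single-procedure patients, while for repeat-procedure patients they count. Third, the protocol's calendar range ends three days before its own 3–10 day rule does for on-schedule procedures, and cannot fit any procedure postponed to Day 19 or later.

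The scope is a descriptive safety table and the scheduling text behind it. The primary endpoint and the tested secondary endpoints do not use these assessments. How many scans or thromboses would change category cannot be derived from the documents. The second defect rests on reading 6.3 as the definition of the post-procedure visit for single-procedure patients, which is the only definition the SAP gives.

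**What to change.** In SAP 6.3 and 10.7:

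- State that a negative scan on the day of the procedure cannot serve as the scheduled post-procedure result, and say whether a same-day Doppler enters that visit.
- Count a thrombosis found on any scan after the primary procedure as an event, for single- and repeat-procedure patients alike. Include a same-day positive unless its recorded time shows that it preceded the procedure. Protocol 7.4 records the start time of the procedure, but 7.7.2 lists only the date and method of imaging, so the scan time would have to come from source records where it exists.
- Use the 3–10 day window only to select the scheduled result, and name the rule for choosing among several scans within it, since it has no target day.

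In protocol 7.7.2–7.7.4, Days 12 to 21 and the 3–10 day rule must be reconciled, including for postponed procedures.

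The cost is a few sentences in the SAP, a little programming and one protocol clarification. No added data collection is required.

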11. INTERIM ANALYSES

No interim analyses are planned for this study.

12. PROGRAMMING CONVENTIONS

In principle, displayed digits of calculated summary statistics and percentages will be defined in Table 5.

Table 5 **Displayed Digits of Statistics**

Statistics	Displayed Digits
Number	Integer
Mean, Standard Deviation, 25% quartile, 75% quartile and Median	Rounded to decimal places that are greater than those of the raw data by 1. For data were rounded off to eight decimal places, the required statistics are to be calculated and then rounded off to two decimal places.
Maximum and Minimum	Displayed by respective displayed digits of the raw data. For data rounded off to eight decimal places, required statistics are to be calculated and then rounded off to one decimal place.
Percentage (%)	Rounded to one decimal place.
P-value	Rounded off to four decimal places. Values less than 0.0001 will be reported as <.0001.

13. CHANGES FROM PROTOCOL

- An analysis using the van Elteren is added in order to compare the duration of the increase in platelet count between S-888711 and placebo group for the ITT population (see [Section 9.2.3](#))
- Summary of significant TEAEs is removed because this event was not defined in the protocol.

Appendix 1 Time and Events Schedule

Study Day	Screening		Treatment Period							Post-treatment Period (Invasive Procedure, Days 9 to 14)														With- drawal ^a	Unsche- duled ^b		
	From Day -28	Day 1		Day 2	Day 3	Day 4	Day 5	Day 6	Day 7	Day 8	Day 9	Day 10	Day 11	Day 12	Day 13	Day 14	Day 17	Day 21	Day 28	Day 35							
		Pre- dosing	Post- dosing																								
Informed consent	X																										
Inclusion/exclusion criteria	X																										
Demography (including body weight and height)	X																										
Medical history	X																										
Enrolment (IVRS/IWRS)	X																										
Randomisation (IVRS/IWRS)		X																									
Drug assignment (IVRS/IWRS)											X ^c	(X) ^c	(X) ^c														
Concomitant medication				←																					→		
ECOG performance status	X																										
Type of CLD and severity of liver disorder (Child-Pugh)	X																										
Gastro-oesophageal varices ^d	X																										
Splenomegaly and severity of ascites ^e	X																										
Pregnancy test (urine)	X																									X	X
Physical examination	X	X						X	X	X	X			X			X			X	X	X	X	X ^b			
Portal vein thrombosis assessment ^f	X																	←	X ^g	→					X	X ^b	
Portal blood flow (direction) ^h	X																←	X ^g	→						X	X ^b	
WHO Bleeding Scale	X	X									X				←	X ^g	→				X	X					
Blood pressure, pulse rate	X	X					X			X		X		X		X		X		X	X	X	X	X ^b			
Electrocardiography	X																									X	X ^b
Platelet count (local laboratory)	X	X						X ⁱ	X ⁱ	X ⁱ	X		X		X		X		X	X	X	X	X	X	X ^b		
Haematology except for platelet count (central laboratory)	X	X									X								X						X	X ^b	

Study Day	Screening		Treatment Period							Post-treatment Period (Invasive Procedure, Days 9 to 14)												With- drawal ^a	Unsche- duled ^b
	From Day -28	Day 1		Day 2	Day 3	Day 4	Day 5	Day 6	Day 7	Day 8	Day 9	Day 10	Day 11	Day 12	Day 13	Day 14	Day 17	Day 21	Day 28	Day 35			
		Pre- dosing	Post- dosing																				
Blood chemistry	X	X								X								X			X	X ^b	
Blood coagulation/fibrinolysis assay ^j	X	X								X								X			X	X ^b	
Immunological tests/other tests	X																						
Adverse events	←		→																				
Administration of study medication			X	X	X	X	X ^{c,k}	X ^{c,k}	X ^{c,k}														
Invasive procedure												←	X ^l	→									
Sampling for plasma drug concentration (Sparse PK) ^m							X	X	X														
Sampling for plasma drug concentration (Intensive PK) ⁿ							X	X	X														

a Except for a patient with drug withdrawn because of the administration stopping criterion (ie, platelet count $\geq 50 \times 10^9/L$ with an increase of $\geq 20 \times 10^9/L$ from baseline).

b Only necessary assessments will be performed.

c If platelet count on Day 5, 6 or Day 7 is $\geq 50 \times 10^9/L$ with an increase of $\geq 20 \times 10^9/L$ from baseline, a patient must stop taking study medication.

d Confirmed by upper gastrointestinal endoscopy. If data on upper gastrointestinal endoscopy are obtained within 180 days before randomisation, the data can be used.

e Confirmed by ultrasonography, CT, or MRI. If ultrasonography, CT, or MRI is performed within 28 days before randomisation, the image can be used for assessing the presence or absence of splenomegaly.

f Confirmed by ultrasonography, CT, or MRI in the Screening period and after the invasive procedure. The Screening investigation should be arranged as close to randomisation as possible. However, if gastro-oesophageal varices are treated, portal vein thrombosis will be confirmed with the image obtained after the treatment.

g Performed within 3 to 10 days after the invasive procedure. When any additional invasive procedure is performed, the assessment of bleeding events as graded on the WHO Bleeding Scale, portal vein thrombosis, and portal blood flow will be performed before and after the invasive procedure.

h Confirmed by Doppler ultrasonography (at Screening, the investigation should be as close to randomisation as possible).

i Blood samples will be collected before study medication.

j Antithrombin III activity, fibrinogen, fibrin degradation products, D-dimer, Protein C activity, free protein S antigen, von Willebrand factor activity will be performed only at Screening. Prothrombin time (international normalised ratio value) and activated partial thromboplastin time will be performed at Screening, Day 1, Day 8, Day 14, and Day 35.

k Administered after platelet count is confirmed and drug assignment.

l Performed between Days 9 and 14.

m All patients except for Intensive PK; pre-dose, 2 to 4 hours post-dose on Day 5, and pre-dose on Days 6 and 7.

n At least 20 patients; pre-dose, 2, 4, 6, 8 hours post-dose on Day 5, pre-dose on Days 6 and 7.

Appendix 2 Testing Procedure for Primary and Important Secondary Endpoints

S-888711 for up to 7 days vs. Placebo

Testing the Primary Efficacy Endpoint:

The null hypothesis is that there is no difference between S-888711 for up to 7 days and placebo groups regarding the proportion of patients, who require no platelet transfusion prior to the primary invasive procedure and no rescue therapy for bleeding from randomization until 7 days after the primary elective procedure.

↓ if rejected^a

Testing the Secondary Efficacy Endpoint 1:

The null hypothesis is that there is no difference between S-888711 for up to 7 days and placebo groups regarding the proportion of patients who require no platelet transfusion during the study.

↓ if rejected^a

Testing the Secondary Efficacy Endpoint 2:

The null hypothesis is that there is no difference between S-888711 for up to 7 days and placebo groups regarding the proportion of patients who achieve a platelet count of $\geq 50 \times 10^9/L$ with an increase of $\geq 20 \times 10^9/L$ from baseline at any time during the study.

↓ if rejected^a

Testing the Secondary Efficacy Endpoint 3:

The null hypothesis is that there is no difference between S-888711 and placebo groups regarding the duration of the platelet count $\geq 50 \times 10^9/L$.

↓ if rejected^a

Testing the Secondary Efficacy Endpoint 4:

The null hypothesis is that there is no difference between S-888711 for up to 7 days without platelet transfusion and placebo with platelet transfusion groups regarding the duration of the platelet count $\geq 50 \times 10^9/L$.

[a] If superiority of S-888711 to placebo is demonstrated at the two-sided significance level of 0.05, then the next hypothesis will be tested.

Appendix 3 Calculation p-value and Confidence Interval for Cochran-Mantel-Haenzel Test

Let x_{ij} and n_{ij} denote the number of responders and the total number of patients in treatment i and stratum j , respectively, where $i=1,2$ represents the treatment group (S-888711 or Placebo) and $j = 1,2,3,4$ represents the stratum, the following 2×2 contingency table shows the total number of subjects and the number of responders in each treatment arm at stratum j .

Category	S-888711	Placebo
Response	x_{1j}	x_{2j}
No Response	$n_{1j} - x_{1j}$	$n_{2j} - x_{2j}$
Total	n_{1j}	n_{2j}

The proportion of patients with response (π_{ij}) in treatment i and stratum j can be estimated by:

$$\hat{\pi}_{ij} = x_{ij}/n_{ij}$$

and the stratum-specific proportion difference (d_j) is estimated by:

$$\hat{d}_j = \hat{\pi}_{1j} - \hat{\pi}_{2j}.$$

The adjusted estimate of the difference in the rate of responders between the two treatment groups (d_{adj}) is given as:

$$\hat{d}_{adj} = \sum_{j=1}^4 w_j d_j$$

using the CMH weights defined as $w_j = \left(\frac{n_{1j}n_{2j}}{n_{1j}+n_{2j}} \right) / \left\{ \sum_{j=1}^4 \frac{n_{1j}n_{2j}}{n_{1j}+n_{2j}} \right\}$.

Hence, the 2-sided stratified 95% Wald-type confidence intervals of d_{adj} based on the CMH weights is constructed as:

$$\hat{d}_{adj} \pm z_{\alpha/2} \text{Var}(\hat{d}_{adj}),$$

where the variance of d_{adj} is given as:

$$\text{Var}(\hat{d}_{adj}) = \sqrt{\sum_{j=1}^4 \hat{w}_j^2 \left(\frac{\hat{\pi}_{1j}(1-\hat{\pi}_{1j})}{n_{1j}} + \frac{\hat{\pi}_{2j}(1-\hat{\pi}_{2j})}{n_{2j}} \right)},$$

and $z_{\alpha/2}$ is the 97.5th percentile of the standard normal distribution.

Two-sided p-value will be obtained by:

$$2 \times \left\{ 1 - \Phi \left(\left| \frac{\hat{d}_{adj}}{Var(\hat{d}_{adj})} \right| \right) \right\}$$

where Φ is the cumulative distribution of standard normal distribution.

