8.10.1 Analyses of Efficacy Endpoints

8.10.1.1 Primary Endpoint Analysis

The number and proportion of patients who required no platelet transfusion prior to the primary invasive procedure and no rescue therapy for bleeding from randomisation through 7 days after the primary elective procedure will be calculated by treatment group. The proportion of patients who required no platelet transfusion in the S-888711 group will be compared with that in the placebo group using the Cochran-Mantel-Haenszel test adjusted by the stratification factors.

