6.2 Statistical Testing

Unless otherwise noted, all statistical tests will be performed at a two-sided significance level of 0.05.

A gatekeeping procedure will be employed for sequentially testing the important secondary endpoints (see [Appendix 2](#)). If the primary endpoint is statistically significant, the secondary endpoints will be tested at the 0.05 level (two-sided) in sequence.

Sequential testing for the secondary endpoints will be conducted in the following order:

- The comparison between S-888711 and placebo in the proportion of patients who require no platelet transfusion during the study
- The comparison between S-888711 and placebo in the proportion of responders: patients who achieve a platelet count of $\geq 50 \times 10^9/\text{L}$, with an increase of $\geq 20 \times 10^9/\text{L}$ from baseline at any time during the study
- The comparison between S-888711 and placebo in the duration of platelet count $\geq 50 \times 10^9/\text{L}$
- The comparison between S-888711 without platelet transfusion and placebo with platelet transfusion in the duration of platelet count $\geq 50 \times 10^9/\text{L}$

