9.1.1 Primary Analysis

The number and proportion of patients who required no platelet transfusion prior to the primary invasive procedure and no rescue therapy for bleeding from the date of randomization through 7 days after the primary elective procedure will be calculated by treatment group. The primary endpoint will be presented along with 95% confidence intervals (CIs), which will be calculated with the Clopper-Pearson method.

The proportion of patients who required no platelet transfusion in the S-888711 group will be compared with that in the placebo group using the Cochran-Mantel-Haenszel (CMH) test adjusted by the stratification factors, i.e., the four strata:

- Platelet count at randomization $< 35 \times 10^9/\text{L}$ and liver ablation/coagulation
- Platelet count at randomization $< 35 \times 10^9/\text{L}$ and other invasive procedure
- Platelet count at randomization $\geq 35 \times 10^9/\text{L}$ and liver ablation/coagulation
- Platelet count at randomization $\geq 35 \times 10^9/\text{L}$ and other invasive procedure.

In addition, the differences in the primary endpoint and its 95% CI using Wald method (see [Appendix 3](#)) will be calculated.

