9.2.1.1 Analysis

The number and proportion of patients who required no platelet transfusion during the study will be calculated by treatment group. The proportions will be presented along with 95% CIs. The proportion of patients who required no platelet transfusion during the study in the S-888711 group will be compared with that in the placebo group using the CMH test adjusted by the stratification factors. In addition, the differences in the secondary endpoint and its 95% CI will be calculated.

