9.2.2.1 Analysis

The number and proportion of responders during the study will be calculated by treatment group. The responder rates will be presented along with 95% CIs, which will be calculated with the Clopper-Pearson method. The proportion of responders during the study in the S-888711 group will be compared with that in the placebo group using the CMH test adjusted by the stratification factors. In addition, the differences in the responder rate and its 95% CI will be calculated.

The number and proportion of responders will be calculated by treatment group at each time point. This analysis will be performed for the ITT population with observed values.

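### The SAP names the CMH test for the primary comparison, but its only p-value formula (Appendix 3) is a stratified Wald test

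*SAP*

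**What the plan says.** Protocol 8.10.1.1 says the S-888711 proportion "will be compared with that in the placebo group using the Cochran-Mantel-Haenszel test adjusted by the stratification factors". SAP 9.1.1 repeats this, "using the Cochran-Mantel-Haenszel (CMH) test adjusted by the stratification factors, i.e., the four strata", and lists the four combinations of platelet count at randomisation and procedure type. It then adds an estimate: "In addition, the differences in the primary endpoint and its 95% CI using Wald method". Appendix 3 is cited only at that point, for the interval.

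SAP 9.2.1.1 compares secondary endpoint 1 "with that in the placebo group using the CMH test adjusted by the stratification factors". SAP 9.2.2.1 does the same for endpoint 2: "The proportion of responders during the study in the S-888711 group will be compared with that in the placebo group using the CMH test". Neither section gives a formula or cites the appendix.

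Appendix 3 is headed "Calculation p-value and Confidence Interval for Cochran-Mantel-Haenzel Test". It defines the adjusted difference with CMH weights, a Wald interval around it, and then a p-value: "Two-sided p-value will be obtained by" followed by a normal-tail formula in the ratio of the adjusted difference to the quantity used in the interval. No other p-value formula appears in the SAP.

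The gatekeeping rule in SAP 6.2 is: "If the primary endpoint is statistically significant, the secondary endpoints will be tested at the 0.05 level (two-sided) in sequence". Section 13, which lists changes from the protocol, mentions no change of primary test.

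**The concern.** The CMH test and the Appendix 3 test share a numerator, up to a constant, but not a denominator. A programmer who follows the named test runs standard CMH output. One who follows the appendix, whose title claims to be the CMH calculation, programs a Wald test. Each can point to the SAP, and they will report different p-values. The primary test opens a fixed sequence of four secondary hypotheses, the first two of which are also assigned to CMH. The p-value that decides the study should not depend on which page of the SAP is followed.

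**Working it through.** **Plan's own figure.** SAP 4.3 assumes 70% versus 20%, 100 per arm, two-sided 0.05, and states 99% power. With pooled rate 0.45, the null SE is √(2·0.45·0.55/100) = 0.0704 and the alternative SE is √((0.21+0.16)/100) = 0.0608. Power is Φ((0.50 − 1.96·0.0704)/0.0608) = Φ(5.95) > 99.99%. The stated 99% is met, and 32 per arm would already give 99%.

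**The two statistics.** In stratum j, let x₁, x₂ be successes, n₁, n₂ patients, N = n₁+n₂, m = x₁+x₂, p = x/n and k = n₁n₂/N.

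- Appendix 3: w = k/Σk; d_adj = Σw(p₁−p₂); SE = √Σw²[p₁(1−p₁)/n₁ + p₂(1−p₂)/n₂]; z = d_adj/SE.
- CMH: χ² = [Σ(x₁ − n₁m/N)]² / Σ n₁n₂m(N−m)/[N²(N−1)].

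Since x₁ − n₁m/N = k(p₁−p₂), the CMH numerator is d_adj·Σk before squaring. Only the variance differs: unpooled binomial in Appendix 3, hypergeometric under the null in CMH.

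**Worked example** (constructed; the documents give no stratum sizes). S-888711 3/10, 7/21, 8/21, 13/48; placebo 1/10, 4/20, 3/20, 11/50.

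| Stratum | k | p₁−p₂ | x₁ − n₁m/N | CMH variance |
|---|---|---|---|---|
| 1 | 5.000 | 0.2000 | 1.000 | 0.842 |
| 2 | 10.244 | 0.1333 | 1.366 | 2.061 |
| 3 | 10.244 | 0.2310 | 2.366 | 2.061 |
| 4 | 24.490 | 0.0508 | 1.245 | 4.575 |
| Sum | 49.978 | | 5.977 | 9.540 |

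- Appendix 3: d_adj = 5.977/49.978 = 0.1196; SE = 0.0603; z = 1.984; p = 0.047; 95% CI 0.0015 to 0.2377.
- CMH: χ² = 5.977²/9.540 = 3.744; p = 0.053.

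The decisions at 0.05 are opposite, although every stratum favours S-888711.

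**Other tables.**

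| S-888711 | Placebo | Appendix 3 p | CMH p |
|---|---|---|---|
| 8/25 in each of four strata | 5/25 in each | 0.051 | 0.056 |
| 3/9, 6/16, 7/29, 11/39 | 3/9, 2/26, 3/13, 10/59 | 0.051 | 0.048 |

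The second is the rare reverse case, which needs unequal arms within strata. At the planned rates with 10/20/30/40 per arm (assumed), z is 8.22 by Appendix 3 and 7.03 by CMH.

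**Simulation under the null.** 200 patients, 300,000 trials per cell, five assumed stratum layouts, the same rate in all strata, null rates from 12.5% to 80%.

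| Allocation within strata | Appendix 3 rejects | CMH rejects | Gap (points) |
|---|---|---|---|
| Independent 1:1 split | 5.57–5.74% | 4.91–5.08% | 0.65–0.74 |
| Blocks of 4 (assumed) | 5.54–5.71% | 4.90–5.33% | 0.63–0.68; 0.30–0.48 at 45% |
| Exactly equal arms | 5.42–5.70% | 4.91–5.52% | 0.5–0.7; 0.03–0.04 at 45% |

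Significance by CMH alone did not occur with equal arms or blocks. With independent splits it occurred in 0.04–0.06% of trials at a 12.5% null rate and in about 0.01% or fewer at the other rates.

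**Simulation with an effect** (control 20%, independent splits). Significant by Appendix 3 only: 2.2% of trials at a 12-point difference (power about 50%), 1.1% at 20 points, 0.08% at 30, at most 0.001% at 40, and none at the planned 50 points in 1.5 million trials.

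**The case against.** The strongest reply is that the p-value is already fixed. Appendix 3 is specific, was added in SAP version 2.0, and says how the p-value is to be obtained, while 9.1.1 prints no competing formula. On that reading the test is merely misnamed. This does not settle the matter: 9.1.1 cites the appendix only for the interval, the protocol names CMH, and Section 13 records no replacement.

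A second reply is that the conflict could equally be closed by naming the stratified Wald test in 9.1.1 and listing it in Section 13. That would be coherent and would keep p-value and interval in agreement. It would also depart from the protocol's test and keep the slightly raised error rate.

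Third, the effect is nil at the design difference. That is correct, and it makes this a wording correction.

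Fourth, the simulations assume equal rates across strata. Protocol 8.2 reports 57.1% versus 82.9% by baseline platelet count in the Japanese study's 3 mg group. Using those as null rates in a sparse assumed layout (2/14/8/76 expected per arm) gives 5.8% versus 5.0%, a gap of 0.84 points. So the tabulated ranges are not general, though the direction is the same.

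Fifth, if a stratum has no patients in one arm, the printed formula contains 0/0. This is a fair observation, but it arises only in very sparse layouts.

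**Conclusion.** The point holds. The SAP assigns the primary comparison to the CMH test and prints, under that name, the p-value of a different test. The same ambiguity reaches secondary endpoints 1 and 2. The Appendix 3 value is usually the smaller one, and under the null it rejects about 0.7 points more often than CMH in most of the settings examined, less at a 45% rate when arms are balanced within strata. These figures rest on assumed stratum sizes, an assumed block size and a common rate across strata. The existence of two different p-values rests on none of these, since it follows from the formulas. The study conclusion would not change at the planned effect; for a borderline result it could. The change should be made for the sake of prespecification.

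**What to change.** - In SAP 9.1.1, 9.2.1.1 and 9.2.2.1, state that the p-value deciding each step of the sequence is the standard CMH statistic over the four strata, with 1 df and no continuity correction. The correction must be addressed because it matters: in the worked example it moves the CMH p-value from 0.053 to 0.076.
- Delete the p-value formula from Appendix 3, keep the adjusted difference and its 95% Wald CI, and retitle the appendix to match.
- Relabel 'Var' in Appendix 3 as the standard error. It is printed with the square root, so the arithmetic is right and this is editorial only.

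The cost is wording plus standard software output. The p-value will usually be slightly less favourable than the Appendix 3 value. Exact agreement between p-value and CI is lost: in the worked example the interval, 0.0015 to 0.2377, excludes zero while CMH p = 0.053. The SAP should say that the CMH p-value governs in that case.
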